## 6.4 Analysis of additional outcomes

The analyses of prednisone sparing success, an important secondary outcome, will be analyzed using the methods described for the primary outcome in Section 6.3 with the focus on the cumulative proportion at 1 year. Most of the remaining outcomes will be analyzed using longitudinal analysis techniques or event analysis techniques. Table 2 summarizes the outcome type and corresponding analysis technique for these outcomes with safety outcomes highlighted in italics. Additional details of safety monitoring are provided in Section 7.2.

Table 2. Summary of the type, modeling and frequency of secondary and safety outcomes for the ADVISE trial.							
Outcome Type	Modeling Techniques	Visit Intervals	ADVISE Outcomes				
Continuous							
Person-level	GEE with a linear link Linear mixed effects models	V01-V10 V01, V04, V07, V12	Prednisone dose QoL outcomes (EQ-5D, SF-36, NEI-VFQ)				
Eye-level	GEE with a linear link and bootstrap CIs Linear mixed effects models with a person-specific random intercept	V01-V10 V01, V04, V07, V12	Visual acuity Retinal thickness (log-scale)				
Binary							
Person-level	GEE with a logistic link	V01-V10 V02-V10	Individual level activity (no activity in either eye) Prednisone dose ≤ 7.5 mg				
Eye-level	GEE with a logistic link and bootstrap CIs	V01-V10 V01, V04, V07, V12 V02-V10 V04, V07, V12	Prednisone haltedVA 20/40 or betterVA worse than 20/200Uveitis activityMacular edema (≥ 260µm)Improvement in macular edemaResolution of macular edemaWorsening of macular edema				
Event rates							
Person-level	Negative binomial regression	Real time post randomization	Hospitalization Infections requiring antimicrobial therapy Type-specific infections SAEs				
Time to first event							
Person-level	Kaplan-Meier estimates Cox proportional hazards models	Real time post randomization	Death Hospitalization Infections requiring antimicrobial therapy Type-specific infections SAEs Other Systemia Events				
Eye-level	Frailty models	V02-V10 V02-V10 V04, V07, V12	Decline in VA $\geq$ 6 lines or to NLP or LP New onset macular edema				

Evaluations of repeated binary outcomes (e.g activity, macular edema) and continuous outcomes (e.g. visual acuity) over time will be analyzed using generalized estimating equations (GEE) with Gaussian or logit links

that account for the nested correlations between observations over time and, for eye-specific outcomes, between eyes of the same participant. A saturated mean structure including visit, treatment and visit by treatment interaction terms will be used. The visits that are included in the model depend upon the outcome (e.g. visual acuity V01-V10, corticosteroid sparing V07-V10) and are denoted in Table 2. An unstructured covariance matrix will be used to model the within-individual (or within-eye) repeated measurements. For eye-specific outcomes, the bootstrap will be used to compute standard errors, confidence intervals and p-values to adjust for between-eye correlation. Alternative correlation structures (e.g. exchangeable, AR(1)) will be explored if the unstructured covariance model is unstable

Events will be evaluated in two ways. Time to first event will be graphically explored using Kaplan-Meier curves and comparisons will be made using Cox proportional hazards models for individual outcomes (e.g. prednisone cessation) and frailty models for eye level outcomes (e.g. decline in VA  $\geq$  6 lines). Event rates and comparisons for repeated events (e.g. ocular corticosteroid injections) will be modeled using Negative binomial regression to account for over-dispersion and the model will include a random effect to account for between-eye correlation for eye-specific outcomes.

An important safety consideration is cumulative prednisone exposure, which has been shown to be related to increased risks of cardiovascular disease and mortality. A variety of techniques will be used to monitor cumulative exposure. First, the longitudinal pattern of prednisone dose will be modeled using the techniques described above. Using these models, the population estimates of the cumulative dose over the lifetime of the trial will be computed by adding the dose estimates for each treatment group. Model-based estimates of 95% confidence intervals and treatment comparisons will be calculated. This method uses model-based approaches to adjust for missed visits and loss to follow-up. Alternately, multiple imputation will be used to 'fill in' the doses as the missed visits. Important factors in the imputation include, but are not limited to, prednisone dose at adjacent visits (given the rigorous nature of tapering regimes) and activity. Once the missing doses have been 'filled in' the cumulative usage can be calculated directly for each participant and standard analytic techniques can be used to compare the two treatment arms. Multiple iterations ensure that the analysis takes into account the uncertainty in the imputed values.

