#### 6.0 Statistical Analysis Methods

#### 6.1 General principles

The primary analyses will include adjustment for randomization strata (immunotherapy use and prednisone dose). Additional analyses that are unadjusted or are adjusted for potential confounders will also be performed as secondary analyses. Robust standard errors will be computed using statistical program-based approaches when available and a bootstrap with the individual as the sampling unit when a pre-programmed approach is not available. All statements of statistical significance and confidence intervals will be based upon a 2-tailed test with a 0.05 level of significance, unless stated otherwise. Key analyses will be duplicated by a second statistician. All analyses will be performed using SAS version 9 or higher, STATA or R.

Prior to formal testing, exploratory data analyses including graphical techniques (e.g. histograms, scatter-plots, boxplots, spaghetti and lasagna plots) and summary statistics (e.g. median, IQR, proportion) will be used to examine cross-sectional and longitudinal patterns in the data as well as identifying potential violations of the assumptions underpinning formal testing, which can help guide decisions to apply transformations or alternative methods. In some cases, transformations of raw data have already been identified (e.g. log-transformation for retinal thickness and IOP) and will be implemented. Summaries will be made overall and by treatment group. During model selection and formal testing, graphical (e.g. residual plots) and analytic (e.g. tests of normality, proportional hazards assumptions) methods will be used to detect violations of modeling assumptions.

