#### 6.3 Primary outcome analysis

The primary goal of the trial is to establish whether adalimumab is superior to conventional immunosuppression for corticosteroid-sparing in the treatment of individuals with intermediate, posterior, or pannuveitis. The analysis will focus on the cumulative proportion with a success. Once a success has been achieved, then it will remain fixed for that individual thereafter. A more standard time to event analysis, which allows for censoring due to loss to follow-up, was considered. However, because the time required to taper prednisone to  $\leq 7.5$  mg/day depends substantially on the initial prednisone dose, small imbalances at baseline could influence greatly such analyses despite stratification. Therefore, time to event analyses will be used as sensitivity analyses. The 6-month time frame was chosen to allow sufficient time to observe the primary outcome regardless of the participant's prednisone dose at randomization and is likely to be more robust to imbalances. Multiple imputation will be used to address missing data due to missed interim visits and loss to follow-up.

Since a minimum of two follow-up visits must occur prior to achieving a corticosteroid success and prednisone must be tapered, the first outcome evaluation will occur at 2 months (V03) and will continue for every visit thereafter. Modeling will focus upon the period between 6 months and 1 year due to the potential for imbalances in the tapering patterns described above. Generalized estimating equations (GEE) will be used to fit logistic regression models comparing the two treatment groups over time while accounting for the correlation between replicate measurements. A saturated mean structure including visits starting at 6 months (V07-V10), treatment, and visit by treatment interaction terms plus the two stratification variables (baseline immunotherapy and initial prednisone dose) will be used. The mean model structure is:

$$logit(Y) = \beta_0 + \beta_1 A + \beta_2 P + \beta_3 S + \beta_4 V_7 + \beta_5 V_8 + \beta_6 V_9 + \beta_7 V_{10} + \beta_8 I_7 + \beta_9 I_8 + \beta_{10} I_9 + \beta_{11} I_{10}$$

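### SAP 6.4 names neither the randomization strata nor the starting prednisone dose in the cumulative-prednisone analysis, which gives up precision unless SAP 6.1 is meant to cover the strata

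*SAP*

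**What the plan says.** Prednisone exposure through 1 year is a listed secondary outcome (Protocol 3.4.2, SAP 4.2), and SAP 6.4 singles out cumulative exposure as a safety matter. It plans two routes.

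- **Model-based.** SAP 6.4 says that "the longitudinal pattern of prednisone dose will be modeled using the techniques described above", and the arm totals "will be computed by adding the dose estimates for each treatment group". The techniques referred to are the repeated-measures models of the same section: "A saturated mean structure including visit, treatment and visit by treatment interaction terms will be used".
- **Imputation-based.** After missing doses are imputed, each patient's total is calculated and "standard analytic techniques can be used to compare the two treatment arms". No covariates are named.

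For the primary outcome, SAP 6.3 gives the same kind of saturated model, but "plus the two stratification variables (baseline immunotherapy and initial prednisone dose) will be used".

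Two sentences in SAP 6.1, under general principles, bear on this: "The primary analyses will include adjustment for randomization strata (immunotherapy use and prednisone dose"), and "Additional analyses that are unadjusted or are adjusted for potential confounders will also be performed as secondary analyses".

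On starting dose, SAP 6.3 says that the time needed to taper "depends substantially on the initial prednisone dose, small imbalances at baseline could influence greatly such analyses despite stratification". It gives this as the reason for making time-to-event analysis a sensitivity analysis.

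**The concern.** Two prognostic baseline variables are at hand, and the section that analyses prednisone exposure mentions neither.

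The first is the pair of randomization strata. Allocation is balanced within them, so a linear analysis that ignores them reports a standard error that is too large. The second is the starting dose itself. The stratum records only whether it is below 30 mg/day or not, and doses from 30 to 60 mg/day sit together in the upper level. A chance difference in starting dose within that level is not removed by a stratum indicator.

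The SAP recognises this dependence for time to success, yet plans an exposure comparison that shares it without a dose covariate. What is at stake is the width of the confidence interval on a secondary outcome that the SAP links to long-term risk. In an unmasked trial, an unstated covariate set also leaves that choice open until the data are seen.

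**Working it through.** **1. Does any rule carry the strata into this analysis?** SAP 6.4 extends the 6.3 methods to prednisone-sparing success only. Protocol 8.3 extends the primary structure to the secondary hypotheses; those listed in Protocol 2.2 and 8.1 are corticosteroid sparing and prednisone discontinuation by one year, not exposure. That leaves SAP 6.1. Its reference to primary analyses could mean the main analysis of every outcome, or only that of the primary outcome.

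**2. Does listing the baseline visit adjust for starting dose?** SAP Table 2 lists V01-V10 for prednisone dose, so baseline dose enters as a response. With complete data a saturated visit-by-treatment model returns the raw arm means; in a check both gave a difference of -149.24. It therefore adjusts for nothing. In an illustrative simulated trial of 222 patients, the standard error of the difference was 267 unadjusted, 212 with the strata and 192 with starting dose added.

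**3. The plan's own figure.** The documents give no SD, effect size, power or interval width for cumulative prednisone, so there is none to reproduce. The stated primary-outcome power does reproduce: 111 per arm, 46.1% vs 67.5%, two-sided 0.05 gives 90.1% against the stated 90%.

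**4. Flare-free totals.** The inputs are the taper schedule in Protocol 4.2.2 and a 4-week initial course (Protocol 4.2.1). I assume a 5-week hold at 7.5 mg/day and then 2.5 mg steps every 2 weeks. The total is 7 times the sum of the weekly mg/day values.

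- 60 mg/day: 4×60 + (50+40+30) + (25+20+15) + (12.5+10) + 5×7.5 + 2×5 + 2×2.5 = 495; ×7 = 3,465 mg.
- 30 mg/day: 4×30 + (25+20+15) + (12.5+10) + 37.5 + 10 + 5 = 255; ×7 = 1,785 mg.
- 10 mg/day: 4×10 + 37.5 + 10 + 5 = 92.5; ×7 = 647.5 mg.

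The range is 3,465/647.5 = 5.4-fold. Between 30 and 60 mg/day it is 1,680 mg, or 1,680/30 = 56 mg of total per 1 mg/day of starting dose. A chance difference of 3 mg/day in mean starting dose within the upper stratum would move that stratum's flare-free contrast by 3×56 = 168 mg.

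**5. The same courses with one large flare.** Suppose a reactivation at week 16 is treated at 60 mg/day and the schedule restarts. The totals become 6,772.5, 5,215 and 4,112.5 mg, a 1.6-fold range. The flare adds about 3,300 to 3,465 mg to each total, and starting dose does not predict who flares.

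**6. Effect on the interval.** Adjusted width / unadjusted width = √(1 − R²), where R² is the share of within-arm variance of the 1-year total that the added covariates explain. R² comes from simulating the protocol's dosing rules with 12,000 patients per scenario. Flare risk was set to the documents' failure rates: 25% for adalimumab, and 45% or 60% for conventional treatment by immunosuppression stratum. Four starting-dose mixes were assumed: 25%, 50% or 75% of patients at 60 mg/day, or doses spread evenly from 10 to 60 mg/day. Flare timing, size and number were also assumed. Ranges are across the four mixes.

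| Flare pattern (assumed) | R², strata | Width ratio | R², strata + mg/day | Width ratio |
|---|---|---|---|---|
| One, dose doubled | 0.52-0.54 | 0.68-0.69 | 0.64-0.77 | 0.48-0.60 |
| One, mixed size | 0.21-0.29 | 0.84-0.89 | 0.29-0.39 | 0.78-0.84 |
| One, raised to 60 mg/day | 0.14-0.19 | 0.90-0.93 | 0.18-0.26 | 0.86-0.91 |
| Repeated, mixed size | 0.09-0.10 | 0.95-0.96 | 0.11-0.15 | 0.92-0.94 |
| Repeated, raised to 60 mg/day | 0.05-0.07 | 0.96-0.98 | 0.06-0.10 | 0.95-0.97 |

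Omitting the strata therefore widens the interval by a factor of 1/0.98 = 1.02 to 1/0.68 = 1.47. A different set of assumptions (0.4 to 1.0 flares per patient-year, 1,200 to 1,500 mg each) gave 1.08 to 1.31, inside that range.

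In mg, for one flare of mixed size with half the patients starting at 60 mg/day: SD 1,511, so the unadjusted half-width is 1.96 × 1,511 × √(2/111) = 398 mg. With the strata it is 398 × 0.84 = 334 mg, and with dose added 398 × 0.78 = 310 mg.

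**The case against.** The strongest reply is that the strata are already covered. SAP 6.1 sits under general principles and classes unadjusted analyses as secondary. The 6.4 sentence may also be shorthand: the next sentence cites corticosteroid sparing at V07-V10 as one of its outcomes, and for that outcome 6.3 adds both strata. This stands as far as it goes. A reader might infer that the strata are definitely left out, but the documents do not establish that; they leave it open.

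If the strata are covered, the remaining gain is modest. With one flare of mixed size, adding mg/day takes the width ratio from 0.84-0.89 to 0.78-0.84; with repeated large flares it adds almost nothing. The outcome carries no power claim. Protocol 8.3 allows further adjusted analyses and SAP 6.5 plans subgroups by prednisone stratum, although neither names dose in mg/day as a covariate.

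A third reply concerns the covariate itself. Protocol 3.6 and SAP 3.2 document only the below-30 or at-least-30 category before the arm is revealed. Treatment is unmasked, and Protocol 4.2.1 lets some initial doses be chosen from a range by severity. A dose settled after the arm is known would be a post-randomization covariate, and adjusting for it could introduce bias. This stands and limits the fix.

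The choice of a 6-month proportion over time to event is reasoned in SAP 6.3 and is not at fault.

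**Conclusion.** The point holds as a gap in specification with a precision cost. The 6.4 model names neither the strata nor the starting dose, 6.1 and 6.4 do not settle whether the strata apply, and no stated model uses dose in mg/day. If the strata are omitted, the interval is about 2% to 47% wider than it need be. Dose in mg/day adds a smaller gain. These figures rest on assumed dose mixes and flare patterns and should be read only as a range.

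Two stronger readings are not supported. One is that strata and starting dose largely determine each patient's total. That is so for flare-free courses or flares that merely double the dose (64% to 77% of variance explained), but Protocol 4.5 allows reactivation dosing up to the maximum; the share is then 18% to 39% with one flare of mixed or maximum size and 6% to 15% with repeated ones. The other is that the unadjusted comparison is biased. Randomization keeps it valid, and its interval already allows for chance imbalance in starting dose. This is a cheap improvement, not a threat to the trial's conclusions.

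**What to change.** In SAP 6.4, state that the prednisone-dose model and the per-patient cumulative-dose comparison (ANCOVA within each imputed data set) include both stratum indicators and a prednisone dose in mg/day recorded before the arm is revealed. That should be the planned initial dose if it was recorded then, otherwise the dose being taken at enrollment, and never a dose set after allocation is known. Adjust the time-to-success sensitivity analysis for the same covariates. In SAP 6.1, say whether the strata rule applies to the main analysis of every outcome.

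The cost is SAP wording, a little more analysis work, and a check of which dose was recorded before allocation for patients already enrolled. That check is needed because Protocol 3.6 stratifies on the initial dose in the trial, while SAP 3.2 refers to the dose at randomization. The enrollment dose is the weaker fallback: an active patient not yet on prednisone has a value of zero but starts at the maximum allowed dose under Protocol 4.2.1, so that group would need its own indicator.

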# 3.4.2 Secondary outcomes

Secondary corticosteroid sparing outcomes

- 1. The ability to achieve inactive uveitis and prednisone <7.5 mg/day for 2 consecutive visits >28 days apart within one year of randomization.
- 2. The ability to achieve inactive uveitis and completely discontinue prednisone for 2 consecutive visits >28 days apart within 6 months and one year of randomization.
- 3. Prednisone exposure (e.g., cumulative prednisone dose and/or mean prednisone dose) in the 2 groups over 1 year with emphasis on the 6-month (primary outcome) and 1-year (end of follow-up) visits.

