# 3.7 Data collection schedule

Participants will be followed monthly for 6 months, and every two months thereafter until anniversary study closeout 1 year after randomization. The visit and examination schedule is given in Table 2.

Table 3. Visit and examination schedule										
Month	BL*	1	2	3	4	5	6	8	10	12
Visit ID	V01	V02	V03	V04	V05	V06	V07	V08	V09	V10
All patients										
Visual acuity †	Х	Х	Х	Х	Х	Х	Х	Х	Х	Х
Medical, ophthalmic, and treatment history	Х	Х	Х	Х	Х	Х	Х	Х	Х	Х
Weight and blood pressure	Х	Х	Х	Х	Х	Х	Х	Х	Х	Х
Height	Х									
Eye examination	X	Х	Х	Х	Х	Х	Х	Х	Х	Х
Optical coherence tomography (OCT) +	Х			Х			Х			X
Retinal color photographs ‡	X	V	V	V	V	V	X	V	V	X
Complete blood count & chemistry panel 	X	Х	Х	X	Х	Х	X	Х	Х	X
Quality of life (EuroQoL, SF-36, NEI-VFQ)	X			Х			Х			Х
Disease-specific tests										
Disease Test(s)										
Birdshot chorioretinitis Visual field ¶	Х	Х	Х	Х	Х	Х	Х	Х	Х	Х
Choroiditis (all except birdshot) FAF ∥	Х	Х	Х	Х	Х	Х	Х	Х	Х	Х
VKH, early disease OCT ^	Х	Х	Х	Х	Х	Х	Х	Х	Х	Х
VKH, late disease FAF	Х	Х	Х	Х	Х	Х	Х	Х	Х	Х
Retinal vasculitis and FA #	Х	Х	Х	Х	Х	Х	Х	Х	Х	Х
panuveitis with retinal vasculitis										
Tests to identify exclusion characteristics										
prior to enrollment										
Interferon-y release assay for tuberculosis	Х									
(all patients)**										
Hepatitis B panel % ;hepatitis C antibody (all)	Х									
Gadolinium enhanced MRI for patients with	Х									
anterior/intermediate or intermediate uveitis										
without systemic disease only ††										
Pregnancy test for women of child bearing	Х									
potential										
* BL = baseline		.								
† Evaluation of best corrected visual acuity after st	andard	refracti	on							
 UCT centered on tovea  9 field 50 or 60° photographs or wide field photog	aranh (e		tos)							
§ Including creatinine liver enzymes and serum du	ucose	.g., op	103)							
¶ Either quantitative Goldmann perimetry or autom	nated pe	rimetry	with H	lumphr	ev SIT.	A-fast 3	30-2 ar	nd Scre	ening	P60
may be used, but once chosen, the visual field test	ing shou	uld be t	he san	ne for a	all visit t	for eac	h indivi	idual pa	atient	
FAF= fundus autofluorescence										
^ OCT centered on fovea & additionally, as needed	d, OCT (	centere	d to ca	pture a	area wi	th grea	itest su	bretina	l thickr	iess

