Active, not on prednisone	Maximum allowed dose (1 mg/kg/day if < 60 kg OR 60 mg/day if ≥ 60 kg)	Controlled: Taper Not controlled: Hold at current dose	Controlled: Taper Substantially improved ‡ : Taper, but not below 7.5 mg/day until inactive.Only advance immuno.suppression if control is not achieved after 4 more weeks. Not controlled: Taper but not below 7.5 mg/day and advance immunosuppression				
Reactivated, on prednisone	Current dose ≥ ½ maximum allowed dose§: Increase to maximum allowed dose Current dose < ½ maximum allowed dose: Increase to between double current dose and maximum allowed dose depending on severity	Controlled: Taper Not controlled at maximum dose: Hold at maximum dose for 2 more weeks Not controlled while below maximum dose: Increase to maximum dose for 2 weeks	Controlled: Taper Substantially improved ‡ : Taper.but not below 7.5 mg/day until inactive. Only advance immunosuppression if control is not achieved after 4 more weeks. Not controlled: Taper,but not below 7.5 mg/day until inactive and advance immunosuppression				
Inactive, on prednisone > 7.5 mg/day	Hold at dose at enrollment	Controlled: Continue on same dose Not controlled (i.e. reactivates): Follow instructions for 'Reactivated, on prednisone'	Controlled: Taper Not controlled (i.e. reactivates): Follow instructions for 'Reactivated, on prednisone'				

\* If the study ophthalmologist does not expect the uveitis to be controlled at 2 weeks, then an initial course of 4 weeks of prednisone can be prescribed. The first assessment of activity would occur at the next scheduled visit (i.e. in 4 weeks).

+ If the study ophthalmologist expects the uveitis to be controlled at 2 weeks, then the corticosteroid taper can be automatically initiated at 2 weeks without a clinic visit. The first assessment of activity would occur at the next scheduled visit (i.e. in 4 weeks)

‡ Substantially improved such that uveitis is expected to be controlled by the next visit

§ The maximum allowed dose is 1 mg/kg/day for participants < 60 kg and 60 mg/day for participants ≥ 60 kg

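### SAP 6.4 totals prednisone from one dose per visit, which misstates flare courses that change weekly between visits; the total should be built from dated doses

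*SAP*

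**What the plan says.** Protocol 3.4.2 lists as secondary outcome 3: "Prednisone exposure (e.g., cumulative prednisone dose and/or mean prednisone dose) in the 2 groups over 1 year". SAP 6.4 gives two ways to obtain the cumulative dose.

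- Model route: prednisone dose at V01-V10 is modelled (SAP Table 2), and the cumulative dose is "computed by adding the dose estimates for each treatment group".
- Imputation route: "multiple imputation will be used to 'fill in' the doses as the missed visits". On the predictors it says: "Important factors in the imputation include, but are not limited to, prednisone dose at adjacent visits". After that, "the cumulative usage can be calculated directly for each participant and standard analytic techniques can be used to compare the two treatment arms".

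Neither route mentions doses between visits, dated dose changes, or whether a visit's dose is the one before or after that day's change.

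On timing, Protocol 3.7 says: "Participants will be followed monthly for 6 months, and every two months thereafter until anniversary study closeout 1 year after randomization". The tapering schedule (Table 4, Protocol 4.2.2) lowers the dose every week above 7.5 mg/day and every two weeks below it. Protocol 4.5 at least doubles the dose on reactivation during the taper, up to the maximum allowed. If control is expected, "then the corticosteroid taper can be automatically initiated at 2 weeks without a clinic visit"; the footnote to Table 6a applies the same rule to reactivations. Protocol 3.4.3 says that treatment decisions have to be made at the participant's visit.

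**The concern.** A visit-day dose is not the dose taken over the weeks that follow. When a flare is found at a visit, the dose rises that day and then falls in weekly steps before the next visit. If the arrival dose is recorded, much of the course lies between two low readings. If the leaving dose is recorded, the peak is spread over days when it was not taken. The sampling times are tied to the dose changes, so the result can be bias and not only noise. Multiple imputation and model-based intervals do not touch it.

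Adalimumab is hypothesised to be superior in corticosteroid sparing, so the arms may well differ in flares and re-escalations, and these are what visit-day sampling measures worst. The reported prednisone saving could then be too small or too large, depending on a convention that neither document states.

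**Working it through.** **Inputs from the documents.** Visits at months 0-6, 8, 10 and 12 (Protocol 3.7). Taper steps of 10, 5 and 2.5 mg weekly down to 7.5 mg/day (Table 4). Raised dose held for 2 or 4 weeks before tapering (Tables 3 and 6a, with footnotes). The plan gives no figure for cumulative prednisone. All estimates below use exact interval lengths, and the trapezoid rule unless stated.

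**Check of the dose path.** From 60 mg/day, eight weekly steps at 50, 40, 30, 25, 20, 15, 12.5 and 10 lead to 7.5, followed by 4 weeks at 7.5. A 2-week hold gives 2 + 8 + 4 = 14 weeks and a 4-week hold gives 16. Protocol 4.2.2 states 15 weeks, which lies between.

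**One interval after a flare** (illustration: off prednisone, restarted at 60 mg/day at month 10, held 2 weeks, 61 days to month 12).

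- Taken: 60×14 + 7×(50+40+30+25+20+15) + 5×12.5 = 840 + 1,260 + 62.5 = 2,162.5 mg.
- Arrival doses: (0+12.5)/2 × 61 = 381 mg, or -82%.
- Leaving doses, trapezoid, months 8-12: (0+60)/2 × 61 + (60+12.5)/2 × 61 = 1,830 + 2,211 = 4,041 mg, or +87%.
- Leaving dose carried forward: 60 × 61 = 3,660 mg, or +69%.

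**Range for single courses.** The start was 0 or 7.5 mg/day, the peak 15, 30 or 60 mg/day, the hold 2 or 4 weeks, and the interval 30 or 61 days.

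- Arrival doses undercount the interval after the flare by 26-82%. The mildest case (from 7.5 to 15 mg/day, 2-week hold, 61 days) is 15×14 + 12.5×7 + 10×7 + 7.5×33 = 615 mg taken, against 7.5×61 = 457.5 mg.
- Leaving doses in a trapezoid overcount the two intervals around the flare by 11-89%.
- Leaving doses carried forward overcount the interval after it by 1-69%.
- Using both doses (leaving at the start of the interval, arrival at its end) gives -13% to +12%.

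**Full year for the illustrated record** (60 mg/day at entry, 2-week hold, tapered off, flare at month 10). The true total is 4,915 mg. Arrival doses give 3,035 mg (-38%) and leaving doses 6,589 mg (+34%). The same start without a flare gives -4% and -6%, so the flare drives the error. If V01 holds a pre-trial dose of 0, the arrival total falls by 60/2 × 30 = 900 mg to 2,135 mg (-57%).

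**Difference between arms.** The documents give no flare rates, so these are assumed: 0.15 vs 0.06 and 0.08 vs 0.03 flares per month (conventional vs adalimumab); low, mixed or high flare doses; 2- or 4-week holds; 2,500 simulated patients per arm per scenario.

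| Flares starting on a scheduled visit day | Error, leaving dose recorded | Error, arrival dose recorded |
|---|---|---|
| All | +24% to +55% | -23% to -52% |
| Half | +13% to +28% | -9% to -24% |
| None (starts unrelated to visits) | -2% to +5% | -2% to +5% |

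One scenario as an example (0.15 vs 0.06, mixed doses, 2-week hold): with all flares starting at visits the true difference is 990 mg and the errors are +48% and -47%. With none, it is 1,132 mg and the errors are 0% and -1%.

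**The case against.** The strongest reply is that the data may already suffice. Treatment history is taken at every visit (Protocol Table 2). Forms are to capture the detail needed to assess adherence to the treatment guidelines (Protocol 10.2.1), and SAP 7.2 compares actual treatment with the criteria each month. The case report form is not among the documents, so a reader may not infer that dated changes are missing. This stands, and it makes the fix cheap. It does not put those data into SAP 6.4, whose stated steps use visit doses.

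A reader might also infer a fixed bias, for example about 40% of the arm difference. The documents do not support that. Such a figure needs assumed flare rates and nearly every flare starting on a scheduled visit day; without that link, the error is close to zero. Nor is a flare course always mostly over by the next visit: 30 days after a 60 mg/day restart, the schedule leaves 30 mg/day (2-week hold) or 50 mg/day (4-week hold).

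Part of the trapezoid overcount is an interpolation artefact. In the illustration, 1,830 mg falls in months 8-10, before the flare, while months 10-12 are only 2% too high. This is correct, but carrying the dose forward moves the error to +69% after the flare. The near-unbiased version needs both an arrival and a leaving dose, which the SAP does not provide for. The absence of stated interval weights in the model route is a separate gap.

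Finally, the week-2 decision in Tables 3 and 6a may bring extra contacts, and the outcome is secondary and worded with latitude. Both points limit the stakes but leave the method as written.

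**Conclusion.** The point holds as a weakness in the derivation of a named secondary and safety outcome. One dose per visit, even with interval weights, misstates flare courses that start at visits. For the arm difference the documents support only a conditional range: -2% to +5% if flare starts are unrelated to visit days, about 9-28% in size if half start on visit days, and about 23-55% if all do. If the conventional arm flares more, as assumed here, arrival doses understate the prednisone saving with adalimumab and leaving doses overstate it. Flare rates, flare-dose mix and the share starting at visits are assumptions. An error from recording a pre-trial dose at V01 should largely cancel between randomized arms, but would distort each arm's total.

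**What to change.** In SAP 6.4:

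- Define each participant's cumulative prednisone as the sum of dose taken × days at that dose, from randomization to month 12, starting from the initial trial dose.
- Build it from dated dose changes in the treatment history already taken at every visit. Where dates are not captured, use both the arrival and the leaving dose at each visit plus the prescribed taper.
- Compare arms on this total, and on total divided by days for the mean dose.
- Impute missing between-visit intervals, not visit-day doses.
- Keep the V01-V10 model only to describe dose at each visit.

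The cost is SAP wording, a derivation program, some data entry, and some recall error in dates. It needs no extra visits, tests or patients. Because the trial is unmasked, the rule should be fixed before the exposure data are analysed.
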